# 6. PROJECT MANAGEMENT

The study is sponsored by University College London (UCL) and the governance and management of the study will be undertaken by UCL. There are several parties involved in project management: UCL (study governance and data collection); NWORTH (randomization, trial analysis) and Swansea (health economics analysis). Study-specific SOPs will be developed as required and will be addressed throughout the study period and regularly reviewed. Best practice will be employed throughout to ensure the trial is managed to the highest possible standard. Appropriate supervision and training of research staff and training in Good Clinical Practice (GCP) will be ensured.

We have established an independent Trial Steering Committee (TSC), an independent Data Monitoring & Ethics Committee (DMEC) and a Trial Management Group (TMG). The TSC and DMEC will meet at agreed time intervals, which will be documented in the committees' terms of reference or charter. Both will consist of an independent chair and an independent statistician. The DMEC will be able to advise on changes to the conduct of the trial via recommendations to the TSC and will also receive regular safety reports from the TMG.

### 6.1 Trial Steering Committee

The project's TSC will oversee the running of the study on behalf of the sponsor and funder and will have overall responsibility for the continuation or termination of the trial. It will ensure that the trial is conducted in accordance with the principles of GCP and the relevant regulations, and provide advice on all aspects of the study.

### 6.2 Independent Data Monitoring Committee

The project's DMEC will monitor the data and ethics aspects of the study and provide advice on changes to the conduct of the trial via recommendations to the TSC.

### 6.3 Trial Management Group

A TMG will oversee the day-to-day running of the trial and is composed of research team members, including the Chief Investigators, Trial Lead, Programme Manager and Statistician (see Co-I table at the top of this document). In addition, the group may include other members of the trial team with specific expertise, such as PPI Co-Leads and Health Economists. The TMG will meet frequently during set up and subsequently on an agreed periodic basis once the trial is open to recruitment, and will monitor all aspects of conduct and progress, and ensure the protocol is adhered to.

## 6.4. Patient and public involvement (PPI)

Our PPI members will be involved throughout the duration of the study. PPI Co-Leads [name] and [name] will support RDS member involvement with the study. All public-facing documents have been developed following DRC templates established with input from PPI colleagues and RDS members to ensure they are user-friendly and suitable for all levels of literacy skills. The current version of the intervention (which has undergone feasibility testing) has been co-created with input from individuals living at-risk of a familial form of dementia. Additional modules will also be co-created in consultation with EBE.

PPI colleagues and RDS members will be invited to be involved in discussions throughout the trial (e.g., about the development of interview questions for the process evaluation, the interpretation of the research results and the production of a plain English summary and plans for the dissemination of the study findings). The trial team will develop and deliver short and simple research methods sessions if required, e.g. 'what is a randomised controlled trial?' to help colleagues understand this specific research process.

# 7. ETHICS & REGULATORY APPROVALS

This study has been approved by the UCL Research Ethics Committee (Project ID/Title: 8545/008: Improving wellbeing in at-risk familial dementias (IWARF).

## 7.1 Psychological distress protocol

The study protocol, associated documentation, and all substantial amendments thereof will be submitted for review by UCL Research Ethics Committee (REC). The main ethical concern for the trial is the potential for psychological distress. As part of this study we are inviting people living at-risk of inheriting a form of dementia to engage with exercises which relate to their experience of this and to respond to questions about their experience interacting with an intervention which aims to provide support for this. In doing so, there is a risk that participants could become distressed when particular topics arise the in modules/questionnaires (e.g. survivors' guilt for individuals who have tested negative for inheriting the gene, who may have a sibling who has tested gene-positive and will inherit the dementia). We have a protocol in place in a situation whereby a participant becomes distressed about an aspect of a research visit or intervention. This protocol ensures all researchers are able to follow standardised procedure. The steps being taken to reduce and manage these risks is outlined in the following protocol, detailed below, and included within UCL-REC-approved documents relating to this study. This protocol ensures all researchers can follow standardised procedure.

The protocol is outlined as follows:

- (i) This project is supervised by [name] and [name], both of whom are experienced research psychologists with counselling and clinical psychologist qualifications and extensive experience working with this population. The researchers within the project will report to either of the named supervisors' where expressions of emotional distress are conveyed by participants over Zoom/Teams/phone interviews, email communication or responses to questions in surveys. An email trigger will be set up via Qualtrics to alert a member of the research staff to any non-negative answer to the final item of the PHQ-9 (about suicidality), and/or if severe anxiety or depression are indicated. We will also incorporate signposting to mental health services in the end page of the Qualtrics survey, and a member of the research team will send a follow up via email to the participant within 72 hours of receiving the notification. Research team members will document any indications of psychological distress and any follow up action recommended and taken following discussion with senior members of the team. For the process evaluation qualitative interviews, research team members administering the interviews will complete a post-interview form following each interview which will confirm and detail the presence/absence of any cause for concern or incidence of distress.
- (ii) Every report of participant distress will be pro-actively discussed by the research team members collecting/analysing data with [name], [name] and/or [name] on a case by case basis but in general, the steps that follow will apply: if distress is conveyed over email or in a survey response, the participant will be contacted to remind them that participation in the study is voluntary and that they can withdraw at any time and that there is no obligation to respond to any questions that make them upset and will be offered an opportunity to debrief as well as linked to further support resources as appropriate. If distress is conveyed over Zoom/MS Teams/phone interviews, the researcher will offer the participant a break or reschedule for another time and will also remind the participant of their right to withdraw from the study at any time without need to justify why, offer an opportunity to debrief, and signpost to any further support resources as appropriate. Research team members will document any indications of

psychological distress and any follow up action recommended and taken following discussion with senior members of the team.

(iii) In case of controls who may feel disappointed for having been allocated to the control group, the researcher will explain the value of the control group in randomised controlled trials, that this is a methodological requirement. Will also remind the participant that this is a wait-list study and the intervention will become available for them as soon as we finish data collection.

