#### 3.5 Blinding Status of Study Roles within the Trial

### 3.6 Withdrawal of participants

Participants are free to withdraw at any time during the trial without any impact on their future health and care. Participant data collected to the point of withdrawal will be retained and may be used in the analysis set.

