
- 7. The Office of National Statitistics (ONS) measure for loneliness will be used. based on their recommendations (ONS, 2018) that loneliness can be more comprehensively measured if both direct and indirect measures are used. Specifically, the ONS proposes to use one scale that has been assessed as valid and reliable (as well as a measure that will allow participants to say for themselves whether they feel lonely, providing further insight into the subjective feeling of loneliness for different people. The ONS proposes four items to capture different aspects of loneliness; the first three items are from the UCLA 3-item loneliness scale, a very widely used scale with evidence of good reliability and validity (Hughes et al., 2004) (Item 1: "How often do you feel that lack of companionship?"; Item 2: "How often do you feel left out?"; Item 3: "How often do you feel isolated from others?") using a 3-point rating scale (Hardly ever or never, some of the time, Often). The fourth item is a direct question about how often participants feel lonely (Item 4: "How often do you feel lonely?") using a 5-point rating scale (Often/always, Some of the time, Occasionally, Hardly ever, Never).
- 8. Health and social care resource use, including primary care, outpatient appointments , as well as impacts on productivity and other personal costs, will be measured with a participant reported resource use measure (AR-RUM) which has been co-developed with people living at-risk of fFTD/FAD and healthcare professional stakeholders.

Questionnaire	Screening	BL	9 weeks	6 months
Participant information sheet and consent to provide screening responses	Х			
Eligibility check (screening responses)	Х			
Online opt-in consent process		Х		
Demographics		Х		
WEMWBS		Х	Х	Х
GAD-7		Х	Х	Х
PHQ-9		Х	Х	Х
PAGIS		Х	Х	Х
EQ-5D-5L		Х	Х	Х
ICECAP-A		Х	Х	Х
MPFI-24		Х	Х	Х

Table 1. Schedule to list recruitment, consent and which measures are collected at different timepoints.

ONS loneliness measure (UCLA 3	Х	Х	Х
item plus subjective question)			
AR-RUM	Х	Х	Х
SUS		Х	
		[for	
		intervention	
		group only]	

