## 8.3 Confidentiality

All data will be handled in accordance with General Data Protection Regulation (2018). A pseudonymised version of the datasets will be made available in line with our funder requirements. Audiovisual recordings containing personal identifiers will be substituted for pseudo names during transcription. The transcription service will be a UCL-approved third party.

All trial staff and members of the research team will preserve the confidentiality of participants taking part in the trial, and the Sponsor is registered as a Data Controller with the Information Commissioners Office. The only exception to this would be in the event of a safeguarding whereby the researchers observe or hear anything that causes very serious concern about the participant's health, safety or well-being, or that of another person. If this happens, the researchers have a duty to inform an appropriate professional and will contact

the lead investigator of this study in the first instance. This has been explicitly outlined in the Participant Information Sheets.

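### In-survey signposting to mental health services is described only for the last page, so someone who silently abandons the survey has no described route to it, and it is not stated whether the distress alert runs on part-completed surveys

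*Protocol*

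**What the plan says.** Protocol section 7.1 accepts that "there is a risk that participants could become distressed when particular topics arise the in modules/questionnaires". It then describes three ways in which a survey respondent may reach support.

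- **Signposting in the survey.** "We will also incorporate signposting to mental health services in the end page of the Qualtrics survey". No start page, mid-survey page or early-exit page is mentioned.
- **Automatic alert.** "An email trigger will be set up via Qualtrics to alert a member of the research staff". It covers any non-negative answer to the last PHQ-9 item, and indicated severe anxiety or depression. A follow-up email to the participant is due within 72 hours of the notification.
- **Personal contact.** Where distress is conveyed by email or in a survey response, staff contact the participant. They remind the person that "there is no obligation to respond to any questions that make them upset and will be offered an opportunity to debrief", and link them to further support.

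Section 3.6 adds that "Participants are free to withdraw at any time during the trial without any impact on their future health and care". Section 4.5.2 lists the measures in Table 1, and section 4.5.3 says that all questionnaires are collected through Qualtrics.

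**The concern.** A page at the end of a survey is seen only by those who get there. People who break off because the content upset them are among those the signposting is meant for, and they miss it. The other two routes start only when the team receives a signal. Closing a browser window sends none that the protocol describes.

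The alert raises a related question. It is the main safeguard for a positive answer on suicidality, yet the protocol does not say whether it acts when the answer is given or only when the survey is submitted. If the latter, a participant who gives an alerting answer and then stops would miss both the alert and the last page.

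What is at stake is participant safety and the completeness of a safeguard that the protocol presents as standardised. The primary analysis is not affected.

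**Working it through.** The protocol states no figure to reproduce. The check is a reading of the routes by type of participant, followed by an item count.

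**1. Who reaches what (section 7.1)**

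- (a) *Skips an upsetting item and carries on.* Reaches the last page and sees the signposting. No gap.
- (b) *Gives an alerting answer, then stops.* Misses the last page. Is followed up if the alert runs on unfinished surveys, which is not stated. Undetermined.
- (c) *Conveys distress by email or in a survey response, then stops.* Misses the last page, but is to be contacted, offered a debrief and linked to support. Covered, provided that staff see a response in an unfinished survey.
- (d) *Stops with no alerting answer and without conveying distress.* Misses the last page, and section 7.1 describes no other route. Gap.

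**2. Whether other contacts in the protocol close case (d)**

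- *Baseline.* Under section 3.3 a participant is randomised only after completing baseline measures. Someone who abandons the baseline survey has therefore not reached the check-ins (section 4.1) or the control arm's signposting to usual support (section 4.2).
- *9 weeks.* Section 4.5 places this survey about one week after the third check-in, and section 4.1 allows up to three. In the intervention arm no planned check-in follows it.
- *6 months.* No check-in is planned after this survey in either arm.
- *Control arm.* Its signposting comes after randomisation, points to usual support such as the Rare Dementia Support website, and is not described as signposting to mental health services.

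**3. How much of the survey lies between the PHQ-9 and the last page**

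Inputs are the item counts in sections 4.5.1 and 4.5.2. The order is assumed to be that of Table 1, whose caption ("Table 1. Schedule to list recruitment, consent and which measures are collected at different timepoints") makes no claim about order of administration.

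- Up to and including the PHQ-9: WEMWBS 14 + GAD-7 7 + PHQ-9 9 = 30.
- After it: PAGIS 26 + EQ-5D-5L 6 (five dimensions and the visual analogue scale) + ICECAP-A 5 + MPFI-24 24 + loneliness 4 = 65.
- Share after the PHQ-9: 65 / (30 + 65) = 65/95 = 68%.
- At 9 weeks in the intervention arm, with the 10 usability items: (65 + 10) / (95 + 10) = 75/105 = 71%.

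The resource-use form would add to the items after the PHQ-9, but its length is not given. The PAGIS is used in an adapted version, and 26 is the length stated.

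Range: if the PHQ-9 came last, no scale items would follow it and case (b) would hardly arise. Case (d) would remain, because anyone who stopped before the end would still miss the page.

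**The case against.** The strongest reply is that the last page is one of three routes and that the others are substantial: an alert, a follow-up email, report to a supervisor, case-by-case discussion, personal contact, an offered debrief and links to support. This stands for anyone who sends a signal. It does not reach case (d), and for case (b) it depends on a setting that the protocol does not state.

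A second reply is that support details may be given elsewhere. The baseline survey homepage links to the participant information sheet, which is not shown, and section 7.1 refers to ethics-approved documents that are also not shown. This stands as a limit: one cannot say that early leavers receive no support information at all.

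A third is that survey layout need not be fixed in a protocol. That is fair in general, but this protocol does fix the placement, and does so for its main ethical concern.

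Four stronger readings are tempting and are not supported.

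- *That step (i) and step (ii) of section 7.1 contradict each other.* The statement that "there is no obligation to respond to any questions that make them upset" is not an in-survey instruction. It is a reminder given by staff after distress has been conveyed, in a contact that itself offers support.
- *That people who leave a question unanswered lose the signposting.* They do not, if they continue to the end.
- *That people screened out as ineligible are better served, because their exit page gives a support contact.* That page too is reached only by completing a step, so it sets no higher standard.
- *That section 7.1 conflicts with section 8.3, where "the researchers have a duty to inform an appropriate professional and will contact" the lead investigator first.* Section 8.3 concerns a graver trigger, very serious concern for someone's safety, and can sit on top of section 7.1. Names are removed, so the supervisors in 7.1 and the lead investigator may be the same people.

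**Conclusion.** The point holds in a narrow form. As written, the survey's signposting to mental health services depends on finishing the survey, and a participant who abandons it without sending a signal has no other route in section 7.1. Whether someone who gives an alerting answer and then stops is picked up cannot be determined from the protocol.

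The number affected cannot be estimated, because the protocol gives no rate of survey break-off or of distress. The 68% describes how long the remaining survey is under the assumed order. It is not a measure of harm. The gap applies in both arms and at all three assessments.

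The conclusion rests on two assumptions: that no other in-survey placement exists beyond what section 7.1 describes, and that documents not shown do not already close the gap.

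**What to change.** Two changes, both to survey build and wording.

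1. Show the existing signposting text where it does not depend on finishing, for example on the first page, on the page after the PHQ-9, or in a footer on each page. Keep it on the last page as well, and amend section 7.1 to say so.
2. State in section 7.1 whether the alert runs on part-completed responses. If it does not, set it so that it does. Test it with a survey abandoned directly after an alerting answer, and keep a record of the test.

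A cross-reference between sections 7.1 and 8.3 would help staff but is optional.

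The cost is a small change to the survey and a few lines of text, with no extra visits. It should be made identically in both arms so that exposure to the text does not differ by allocation. No alert threshold, response time or clinical content needs to change, and none is proposed.

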## 7.2 Reward and recognition for participants

All participants enrolled in the trial will receive a £15 voucher for a range of online shops as a gesture of appreciation for their contribution to research.

# 8. DATA MONITORING

## 8.1 Quality Assurance (QA) and Quality Control (QC) of data

QA includes all the planned and systematic actions established to ensure the trial is performed and data generated, documented/recorded and reported in compliance with the principles of GCP and applicable regulatory requirements.

QC is the operational techniques and activities undertaken within the quality assurance system to verify that the requirements for quality of the research-related activities are fulfilled.

## 8.2 Monitoring plan

A Monitoring Plan will be prepared prior to participant recruitment detailing the monitoring strategy for the trial. The plan will include requirements for day-to-day centralised monitoring.

## 8.3 Confidentiality

All data will be handled in accordance with General Data Protection Regulation (2018). A pseudonymised version of the datasets will be made available in line with our funder requirements. Audiovisual recordings containing personal identifiers will be substituted for pseudo names during transcription. The transcription service will be a UCL-approved third party.

All trial staff and members of the research team will preserve the confidentiality of participants taking part in the trial, and the Sponsor is registered as a Data Controller with the Information Commissioners Office. The only exception to this would be in the event of a safeguarding whereby the researchers observe or hear anything that causes very serious concern about the participant's health, safety or well-being, or that of another person. If this happens, the researchers have a duty to inform an appropriate professional and will contact

the lead investigator of this study in the first instance. This has been explicitly outlined in the Participant Information Sheets.

# 9. DATA HANDLING

Electronic data collected will be downloaded from respective platforms (e.g., Qualtrics, Zoom/Teams) to secure UCL servers and uploaded to the UCL Data Safe Haven. The Data Safe Haven has been certified to the ISO27001 information security standard and conforms to NHS Digital's Data Security and Protection Toolkit. Built using a walled garden approach, where the data is stored, processed and managed within the security of the system, avoiding the complexity of assured endpoint encryption. A file transfer mechanism enables information to be transferred into the walled garden simply and securely.

Researchers will complete UCL Data Safe Haven training, including learning how to securely upload scanned/electronic data from their research sites onto the repository. Personal details (e.g., participant name and contact details) will be available on the Data Safe Haven, alongside a unique participant identifier.

# 11. INDEMNITY

Cover for harm as a result of the design or conduct of the study has been arranged with the study Sponsor (aligned with UCL Insurance provided for research studies: https://ethics.grad.ucl.ac.uk/uclinsurance.php).

# 12. FINANCIAL ASPECTS

This study is funded by the National Institute for Health & Care Research (NIHR) and will be managed in accordance with the relevant policies and procedures.

# 13. DEFINITION OF END OF STUDY

This is defined as the date of the last assessment of the last participant.

# 14. ARCHIVING

UCL recognise that there is an obligation to archive study-related documents at the end of the study (as such end as defined within this protocol). The Chief Investigator confirms that this project's researchers will archive the study master file at UCL in line with all relevant legal and statutory requirements. In line with our funder requirements (see in line with UCL's rules around data retention: https://www.ucl.ac.uk/library/collections/records-office/records-retention/retention-schedule/research-data), we are required to de-identify the data and make this available re-use free of charge, as open data, safeguarded data or controlled data. The access category data is classified as should be selected to minimise the risk of disclosing personal information. This must be deposited within an NIHR-approved data repository 3 months after the grant end date.

The data will be stored at the Dementia Research Centre, UCL. Long-term data archiving will be managed in line with UCL's records office policy.

